CC-4047-MM-002 is a Celgene sponsored phase 1b/2 multi-center, randomized, open-label, dose escalation study that is evaluating the safety and efficacy of oral pomalidomide alone and in combination with low-dose dexamethasone in patients with relapsed and refractory multiple myeloma. Eligible patients must have received at least 2 prior regimens and all patients must have received prior treatment that includes lenalidomide and bortezomib. This study consists of a phase 1 single agent pomalidomide (maximum tolerated dose [MTD]) segment and phase 2 randomized (pomalidomide plus low-dose dexamethasone versus pomalidomide alone) segment. The MTD was 4 mg 21/28 days (there were 4 drug-related DLTs [Grade 4 neutropenia] at 5 mg). Neutropenia and anemia were the most common grade 3/4 toxicities; there was a dose-dependent increase in grade 4 neutropenia. Based on the preliminary safety and response data, 4 mg 21/28 days is the dose for the phase 2 segment.

Pre-clinical data and the prior experience with thalidomide and lenalidomide in the treatment of patients with myelofibrosis with myeloid metaplasia (MMM) provide the rationale for the use of pomalidomide in patients with MMM. This is further supported by the results of a Celgene sponsored trial (MMM-001) which indicated that pomalidomide therapy at 0.5 mg or 2 mg/day +/- an abbreviated course of prednisone is well tolerated in patients with myelofibrosis and active in the treatment of anemia.

1.6 Rationale for the current trial: Clearly patients with EMD and PCL need newer therapies. The combination of pomalidomide and ixazomib provides a potentially powerful combination due to several reasons. We studied 174 consecutive patients with relapsed refractory multiple myeloma (MM) enrolled on a phase II clinical trial of pomalidomide plus low-dose dexamethasone at Mayo Clinic. Extramedullary disease (EMD) was present at the time of trial entry in 7.5% (13 of 174 patients). The response of EMD to pomalidomide plus low-dose dexamethasone included two complete and two partial responses among the 13 patients

(response rate, 31%). The results of this study suggest that pomalidomide can enter the extramedullary sites and attain therapeutic levels, with resultant disease response.

Similar to bortezomib, MLN2238 potently, reversibly, and selectively inhibits the 20S proteasome. However in contrast to bortezomib, it has a shorter dissociation half-life ($t_{1/2}$) that may contribute to increased tissue distribution. Bortezomib has a slowly reversible dissociation rate from the red blood cell proteasome, while MLN2238 demonstrates a more rapidly reversible dissociation rate from the blood but sustained effects on bone marrow and tumor proteasomes suggesting better tissue distribution. The pharmacologic implications of this difference in binding kinetics and tissue distribution may in turn result in differences in safety and efficacy profiles in a broader range of tumors. In xenograft-bearing mice, the more rapid dissociation rate correlates with an increased ratio of tumor proteasome inhibition to blood proteasome inhibition, and ixazomib shows greater antitumor activity in several xenograft models, both solid tumor and bortezomib-resistant xenografts, than bortezomib. This particular property may enable ixazomib to attain higher levels in the extramedullary compartment, thus offer a particular advantage in this clinical situation. Finally, combinations of an IMiD and a proteasome inhibitor have been the most effective regimens in myeloma, as has been seen with bortezomib or carfilzomib combinations with thalidomide or lenalidomide.

2.0 Goals

2.1 Primary

To determine the confirmed response rate (\geq PR) of ixazomib, used in combination with pomalidomide and dexamethasone in patients with previously treated multiple myeloma (MM) with extramedullary disease.

2.2 Secondary

2.21 To determine the toxicities associated with ixazomib in combination with pomalidomide and dexamethasone in patients with previously treated MM with extramedullary disease.

2.22 To determine the differential response rates (biochemical versus extramedullary disease) with ixazomib in combination with pomalidomide and dexamethasone in patients with previously treated MM with extramedullary disease.

2.23 To determine the progression free survival following treatment with ixazomib in combination with pomalidomide and dexamethasone in patients with previously treated MM with extramedullary disease.

2.3 Correlative Research

2.31 To assess the proportion of patients achieving minimal residual disease (MRD) negative status.

3.0 Patient Eligibility

3.1 Registration - Inclusion Criteria

- 3.11 Age ≥ 18 years.
- 3.12 Previously treated myeloma, currently with extramedullary disease (defined as plasmacytoma outside bone marrow that is not contiguous with a bone lesion) with at least one lesion that has a single diameter of ≥ 2 cm or plasma cell leukemia (defined as circulating plasma cells exceeding 5% of peripheral blood leukocytes or $0.5 \times 10^9/L$ or 200 cells/150000 events by flowcytometry).
- 3.13 The following laboratory values obtained ≤ 14 days prior to registration.
- Calculated creatinine clearance (using Cockcroft-Gault equation below)* ≥ 30 mL/min
 - Absolute neutrophil count (ANC) $\geq 1000/mm^3$
 - Platelet count $\geq 50,000/mm^3$
 - Hemoglobin ≥ 8.0 g/dL

*Cockcroft-Gault Equation:

$$\text{Creatinine clearance for males} = \frac{(140 - \text{age})(\text{actual body weight in kg})}{(72)(\text{serum creatinine in mg/dL})}$$

$$\text{Creatinine clearance for females} = \frac{(140 - \text{age})(\text{actual body weight in kg})(0.85)}{(72)(\text{serum creatinine in mg/dL})}$$

- 3.14 Patients with measurable disease defined as at least one of the following:
- For patients with EMD measurable disease by CT or MRI or the CT portion of the PET/CT: Must have at least one lesion that has a single diameter of ≥ 2 cm. Skin lesions can be used if the area is ≥ 2 cm in at least one diameter and measured with a ruler.
 - Plasma cell count $\geq 0.5 \times 10^9/L$ or 5 percent of the peripheral blood white cells
 - Plasma cell count if determined by flow cytometry, $\geq 200/150,000$ events
- 3.15 ECOG performance status (PS) 0, 1 or 2 ([Appendix I](#)).
- 3.16 Provide informed written consent.
- 3.17 Negative pregnancy test done ≤ 7 days prior to registration, for women of childbearing potential only.
- 3.18 All study participants must be registered into the mandatory POMALYST REMS™ program, and be willing and able to comply with the requirements of the POMALYST REMS™ program.
- 3.19a Willing to return to enrolling institution for follow-up (during the Active Monitoring Phase of the study).
- 3.19b Willing to provide bone marrow and blood samples for correlative research purposes (see Sections 6.12 and 14.1).

3.2 Registration - Exclusion Criteria

- 3.21 Other malignancy requiring active therapy.
EXCEPTIONS: Non-melanoma skin cancer, DCIS or carcinoma-in-situ of the cervix.
NOTE: If there is a history or prior malignancy, they must not be receiving other specific treatment for their cancer.
- 3.22 Any of the following because this study involves an investigational agent whose genotoxic, mutagenic and teratogenic effects on the developing fetus and newborn are unknown:
- Females of childbearing potential (FCBP)[†] must have a negative serum pregnancy test with a sensitivity of at least 50 mIU/mL within 10 – 14 days prior to and again within 24 hours prior to prescribing pomalidomide for Cycle 1 (prescriptions must be filled within 7 days as required by RevAssist), and must either commit to continued abstinence from heterosexual intercourse or begin TWO acceptable methods of birth control, one highly effective method and one additional effective method.
AT THE SAME TIME, at least 28 days before she starts taking pomalidomide FCBP must also agree to ongoing pregnancy testing. Men must agree to use a latex condom during sexual contact with a FCBP even if they have had a successful vasectomy.
See [Appendix IV](#): Pomalidomide Education and Counselling Guidance Document. Patient must follow pregnancy testing requirements as outlined in the POMALYST REMS™ program.
 - Nursing women
 - Men or women of childbearing potential who are unwilling to employ adequate contraception
- 3.23 Other co-morbidity which would interfere with patient's ability to participate in trial, e.g. uncontrolled infection, uncompensated heart or lung disease.
- 3.24 Other concurrent chemotherapy, radiotherapy, or any ancillary therapy considered investigational.
NOTE: Bisphosphonates are considered to be supportive care rather than therapy, and are thus allowed while on protocol treatment.
- 3.25 Patient has \geq Grade 3 peripheral neuropathy, or Grade 2 with pain on clinical examination during the screening period.
- 3.26 Major surgery \leq 14 days before study registration.
- 3.27 Systemic treatment with strong CYP3A4 inducers (e.g. rifampin, rifapentine, rifabutin, carbamazepine, phenytoin, phenobarbital, Gingko biloba, St. John's wort) within 7 days before registration.

[†] A female of childbearing potential is a sexually mature woman who: 1) has not undergone a hysterectomy or bilateral oophorectomy; or 2) has not been naturally postmenopausal for at least 24 consecutive months (i.e., has had menses at any time in the preceding 24 consecutive months).

- 3.28 Evidence of current uncontrolled cardiovascular conditions, including cardiac arrhythmias, congestive heart failure, angina, or myocardial infarction within the past 6 months. Note: Prior to study entry, any ECG abnormality at screening must be documented by the investigator as not medically relevant.
- 3.29a QTc >470 milliseconds (msec) on a 12-lead ECG obtained during the Screening period.
Note: If a machine reading is above this value, the ECG should be reviewed by a qualified reader and confirmed on a subsequent ECG.
- 3.29b Known human immunodeficiency virus (HIV) positive.
- 3.29c Known hepatitis B surface antigen-positive status, or known or suspected active hepatitis C infection.
- 3.29d Any serious medical or psychiatric illness that could, in the investigator's opinion, potentially interfere with the completion of treatment according to this protocol.
- 3.29e Known allergy to any of the study medications, their analogues or excipients in the various formulations.
- 3.29f Known GI disease or GI procedure that could interfere with the oral absorption or tolerance of ixazomib including difficulty swallowing.
- 3.29g Diarrhea >Grade 1, based on the NCI CTCAE grading, in the absence of antidiarrheals.

4.0 Test Schedule

Tests	Days Prior to Registration		Day 8, 15, 22 (Cycles 1-3), Day 15 (Cycle 4 onwards) ¹	Every cycle, pre- treatment ¹	End of Cycle 4 ¹	End of Treatment (+/-14 days) ¹
	≤30 days	≤14 days				
Complete medical history	X					
Adverse Event monitoring		X		X ¹⁶		X
Physical exam, including weight and vital signs		X		X ¹⁶		X
Height		X				
Performance status (ECOG scale)		X		X ¹⁶		X
CBC with differential		X	X	X ¹⁶		X
Chemistry group: sodium, potassium, glucose, alkaline phosphatase; Total and Direct bilirubin; SGOT (AST); serum creatinine, calcium, magnesium		X		X ¹⁶		X
LDH, Beta ₂ -microglobulin, C-reactive protein	X					
Electrophoresis of serum and urine (SPEP/UPEP)		X		X ^{3,16}		X ³
Affected immunoglobulin ²		X		X ^{2,16}		X ²
Immunofixation serum and urine	X			X ^{4,16}		X ⁴
Immunoglobulin free light chain (MML panel)		X		X ^{5,16}		X ⁵
X-ray skeletal survey or low dose full body CT ⁶	X			X ⁶		X
Physical measurement (EMD lesion) ⁷		X		X		
CT Scan, PET/CT, or MRI for measurement of EMD lesion ⁸	X			X ⁸		
Circulating plasma cell assessment (flow cytometry or peripheral smear) ⁹		X		X ^{9,16}		
Bone marrow aspirate and biopsy, myeloma FISH, metaphase cytogenetics, plasma cell proliferation, and flow cytometry	X			X ¹⁰	X ¹⁰	X
Biopsy of extramedullary lesion ¹¹	X					
Chest x-ray	X					
Serum pregnancy test ¹²		X ¹²				
ECG, 12 lead with interpretation	X					
Register patient for POMALYST REMS™ program ¹³		X ¹³				
Patient Medication Diary (Appendix II) ¹⁴				X	X	X
Mandatory tissue block ¹¹	X					
Mandatory Research Bone marrow sample ^R	X			X ¹⁰		X
Mandatory Peripheral Blood sample ^R	X			X ¹⁵		X ¹⁵

Cycle = 28 days {FOOTNOTES CONTINUE ON NEXT PAGE}

- 1) All scheduled visits will have a window of ± 7 days unless otherwise stated.
Note: Baseline labs can be used for Cycle 1, Day 1.
 - 2) Affected immunoglobulin refers to the baseline M-protein type, that is, IgG, IgA, or IgD. Not applicable if patient “non-secretory” or if patient has no heavy chain, i.e. light chain myeloma. Affected immunoglobulin is required after baseline only if it used for disease monitoring instead of SPEP (e.g. IgA myeloma).
 - 3) Urine Electrophoresis required only if used to assess disease response.
 - 4) Immunofixation (IF) needed only in the absence of M-protein to document sCR or CR.
 - 5) Serial light chain required if it is used for disease monitoring (measurable disease at baseline)
 - 6) Skeletal survey/low dose CT not needed at baseline or any other timepoint if PET/CT is done at that timepoint. Otherwise every 365 days (12 months) or more often if clinically indicated.
 - 7) For patients with a clinically palpable lesion.
 - 8) CT or MRI or the CT portion of the PET/CT, same modality should be used at baseline and for serial evaluation. PET/CT scans are required at baseline for all patients with EMD. Assessment of EMD lesions should be performed at end of Cycle 1 and every three cycles or more frequently if clinically indicated. For patients with only skin involvement, skin lesions should be measured with a ruler with images maintained in the medical record.
 - 9) Number of circulating cells may be measured using flow cytometry or peripheral smear as is the standard practice for the institution, but same methodology should be used at every time point. This should be repeated after Cycle 1 and every 2 cycles after that or more often if clinically indicated.
 - 10) At the end of 4 cycles and only required to document CR after that. If a bone marrow was done to confirm CR prior to end of 4 cycles, no further bone marrow examination until the end of treatment.
 - 11) In patients with extramedullary soft tissue disease.
 - 12) For women of childbearing potential only. Must be done ≤ 7 days prior to registration.
NOTE: Additional pregnancy testing is required as a condition of participation in the POMALYST REMS™ program.
 - 13) All study participants must be registered into the mandatory POMALYST REMS™ program, and be willing and able to comply with the requirements of the POMALYST REMS™ program.
 - 14) The diary must begin the day the patient starts taking the medication and must be completed per protocol and returned to the treating institution.
 - 15) At baseline, end of Cycle 4, and at end of treatment. See [Section 14.0](#).
 - 16) Mayo Rochester only: Required evaluations can be done through local facility, phone contact, or by local lab as applicable if patient is unable to return to Mayo facility and is approved by study chair.
- R Research funded (see [Section 14.0](#)). Will be charged to study and not to patient’s account.

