^a All response categories require two consecutive assessments made at anytime before the institution of any new therapy; complete and PR, MR and SD categories also require no known evidence of progressive or new bone lesions if radiographic studies were performed. Radiographic studies are not required to satisfy these response requirements. Bone marrow assessments need not be confirmed. Each category, except for stable disease, will have a working subcategory of “unconfirmed” [prefix ‘u’] to designate first time point at which response category MAY have been achieved if confirmed.

^b Presence/absence of clonal cells is based upon the k/λ ratio. An abnormal k/λ ratio by immunohistochemistry and/or immunofluorescence requires a minimum of 100 plasma cells for analysis. An abnormal ratio reflecting presence of an abnormal clone is k/λ of $>4:1$ or $<1:2$.

^c Positive immunofixation alone in a patient previously classified as CR will not be considered progression.

^d Progressive disease should be confirmed. However, treatment may be discontinued for progressive disease that is unconfirmed per physician discretion. In this case, an objective status of PD should be entered on the measurement form and progressive disease should be reported on the event monitoring form.

^e Does not apply to EMD or PCL

^f In the case where a value is felt to be a spurious result per physician discretion (for example, a possible lab error), that value will not be considered when determining the lowest value.

11.6 Types of Response:

11.61 Biochemical response will be defined as detailed above for serum, urine, and FLC.

11.62 Extramedullary disease response will be defined as detailed above for plasmacytomas and plasma cell leukemia.

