13.0 Treatment/Follow-up Decision at Evaluation of Patient

13.1 Patients who are sCR, CR, VGPR, PR, or SD (or usCR, uCR, uVGPR, uPR) will continue treatment per protocol.

13.2 Patients who develop progressive disease while receiving therapy will go to the event-monitoring phase.

13.3 Patients who go off protocol treatment for reasons other than PD will go to the event-monitoring phase per Section 18.0.

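### The End of Treatment visit schedules no response assessment of extramedullary lesions or circulating plasma cells, so an extramedullary-only response can be left without a scheduled confirmation when a patient stops for a reason other than progression.

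*Combined protocol and SAP*

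**What the plan says.** The Section 4.0 table marks the End of Treatment (EOT) column for electrophoresis, affected immunoglobulin, immunofixation, free light chain, bone marrow and "X-ray skeletal survey or low dose full body CT". It leaves that column blank for the three rows that follow the extramedullary disease: the row beginning "Physical measurement (EMD lesion", the row "CT Scan, PET/CT, or MRI for measurement of EMD lesion" and the row beginning "Circulating plasma cell assessment (flow cytometry or peripheral smear".

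Footnote 8 sets the imaging interval: "Assessment of EMD lesions should be performed at end of Cycle 1 and every three cycles or more frequently if clinically indicated". Footnote 9 sets plasma cell counts after Cycle 1 and then every two cycles. It allows more where clinically indicated and requires the same method throughout. Section 11.1 repeats both intervals and adds no EOT assessment.

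The primary endpoint (Sections 16.11 and 16.311) is a response of PR or better on two consecutive evaluations. Table 11.5, footnote a, states when these may be made: "All response categories require two consecutive assessments made at anytime before the institution of any new therapy". Section 13.3 says: "Patients who go off protocol treatment for reasons other than PD will go to the event-monitoring phase per Section 18.0". The Section 4.2 schedule for that phase names no disease test.

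**The concern.** This is a trial in extramedullary myeloma and plasma cell leukemia. A measurable M-protein is not required for entry (Section 11.1), and Section 12.1 has a category for patients followed by extramedullary disease alone. For them, lesion measurements or plasma cell counts carry the primary endpoint.

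Footnote a would accept a confirming assessment made at the EOT visit if that visit comes before new therapy, but the schedule does not ask for one. Every eligible, treated patient without a major violation stays in the denominator. An extramedullary response seen once and never re-measured is therefore scored as a failure for want of a measurement.

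Three further things are at stake:

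- **CR at EOT.** EOT immunofixation and marrow can support a CR. In a patient with a baseline plasmacytoma or plasma cell leukemia, CR also has a lesion or plasma cell criterion, which the visit does not collect.
- **Goal 2.22.** The biochemical and extramedullary response rates are ascertained unequally at this visit.
- **PFS.** Progression counts from the date it is documented, so progression in an unscanned lesion may be dated late.

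**Working it through.** **1. Gaps in the schedule.** Inputs are the 28-day cycle and the intervals in footnotes 8 and 9, over the first 12 cycles.

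| Assessment | Scheduled at end of cycle | Cycle ends with none | Interval |
|---|---|---|---|
| Lesion imaging | 1, 4, 7, 10 | 2, 3, 5, 6, 8, 9, 11, 12 (8/12 = 67%) | 3 × 28 = 84 days |
| Plasma cell count | 1, 3, 5, 7, 9, 11 | 2, 4, 6, 8, 10, 12 (6/12 = 50%) | 2 × 28 = 56 days |
| Palpable lesion | every cycle | none | 28 days |

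Take a non-palpable plasmacytoma whose PR is first seen on the scan at the end of Cycle 4. The next scheduled scan is at the end of Cycle 7. A patient who stops for an adverse event after Cycle 5 or 6 has no scheduled confirming scan. In plasma cell leukemia the parallel case is a PR first counted at the end of Cycle 3 and a stop after Cycle 4.

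**2. The plan's own operating characteristics.** Section 16.21 stops at 2 or fewer successes in 10 and calls the regimen promising at 10 or more in 27. For success probability p:

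P(positive) = Σ (x = 3 to 10) C(10, x) p^x (1 − p)^(10 − x) · P[Bin(17, p) ≥ 10 − x]

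This gives 0.0994 at p = 0.25, 0.7999 at p = 0.45 and 0.9036 at p = 0.50. The Section 16.24 table prints 0.10, 0.80 and 0.90, so it is reproduced.

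**3. Illustration of a loss.** Let m be the share of all responders who lose confirmation in this way. The documents do not give m. Read 50% as the response rate before the loss, so the observable rate is 0.50 × (1 − m).

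| m (assumed) | Observable rate | P(positive) | Responders lost, of 27 × 0.50 = 13.5 expected |
|---|---|---|---|
| 0 | 0.500 | 0.904 | 0 |
| 5% | 0.475 | 0.859 | 13.5 × 0.05 = 0.7 |
| 10% | 0.450 | 0.800 | 13.5 × 0.10 = 1.4 |

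So about one lost responder in the whole trial is enough to move the probability by several points.

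**The case against.** There is a good case that the gap is narrow, and most of it stands.

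- **Plasma cells.** A reader might infer that circulating plasma cells are not measured at all at EOT. Section 14.1 makes a research blood sample mandatory at that visit, and it is tested by flow cytometry for circulating myeloma cells. What is missing is an assessment designated for response: nothing routes the research result there, and a patient followed by smear could not switch method under footnote 9.
- **Who is affected.** A reader might infer that every responder who stops between scans becomes a failure. Palpable lesions are measured every cycle. PR in Table 11.5 needs only one of its listed criteria, so a patient with measurable M-protein or free light chain can be confirmed biochemically, and those markers are followed every cycle and at EOT where they are used for monitoring.
- **Other routes to a measurement.** Footnotes 8 and 9 permit extra assessments when clinically indicated, and event monitoring runs every 3 months until progression. These soften the gap without closing it, because neither requires a lesion measurement or plasma cell count at treatment end.
- **Size.** A reader might take the 16.24 entries of 0.64 or 0.44 as the real power, by supposing that 20% or 30% of responders are lost. Nothing in the documents supports such a rate. Loss requires several conditions together: no biochemical response, disease not followed at every cycle, a stop for a reason other than progression between assessments, and no extra assessment. Success in Section 16.3 is also already defined as confirmed response, so deducting a loss from 50% means reading that figure in a way the plan does not.
- **Goal 2.22 and PFS.** Most of the inequality between the two response types comes from on-treatment frequency, which an EOT assessment would not change. The plan estimates separate rates and a Kaplan-Meier curve and makes no formal comparison.

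**Conclusion.** The point holds in limited form. The EOT visit has no response assessment for extramedullary lesions or circulating plasma cells, and no other section supplies one. Those exposed are patients whose only response is extramedullary, who are followed by imaging or by plasma cell counts, and who stop between scheduled assessments for a reason other than progression. Such a patient can be scored a non-responder with no second measurement ever scheduled, and extramedullary or plasma cell progression may be dated late.

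The size cannot be fixed from the documents. The fall from 0.90 to about 0.86 or 0.80 rests on an assumed 5% or 10% loss among responders and on reading 50% as the rate before that loss. It illustrates sensitivity and is not the plan's power. The documents support saying that a response can go unconfirmed. They do not show that many will, or that the decision rule is miscalibrated: sample size, significance level and cut-offs all stand.

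**What to change.** Mark the EOT column in Section 4.0 for:

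- (a) physical or ruler measurement of palpable or skin lesions, at the examination already due;
- (b) circulating plasma cells in patients with plasma cell leukemia, by their baseline method, on blood already being drawn;
- (c) PET/CT, for patients followed by PET/CT, in place of the EOT skeletal imaging, unless done within a recent window that the sponsor states or progression is already documented. Footnote 6 already allows the substitution: "Skeletal survey/low dose CT not needed at baseline or any other timepoint if PET/CT is done at that timepoint".

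Add one footnote saying that these are done before any new therapy and can serve as the confirming assessment.

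Items (a) and (b) need no new visit or draw. Item (c) means a costlier scan at one visit for the PET/CT patients, and Section 19.2 lists no research-funded tests, so its funding needs to be settled. For patients followed by CT or MRI, an EOT lesion scan would be an added procedure. The sponsor should decide whether the remaining gap for them justifies it. No change to sample size or decision rules is needed.
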